2.4.2 Target Population Rationale

Target population rationale is described in the background (Section 2.1) and target rationale (Section 2.4.1) sections.

2.4.3 Dose Selection Rationale

The planned doses of AMG 427 in this study are [REDACTED]

[REDACTED] µg. AMG 427 will be administered

as single, short IV infusions (eIV infusion may apply) on D1/D5 or D1/D3/D5/D8 of a 14-day treatment cycle, in which the second dose on day 3 or 5 may be the same or

higher than the dose on day 1. Based on observed safety and tolerability, the day 1 dose may be established as a run-in dose (ie, MTD1), while day 3, 5, or 8 doses may

be subsequently escalated. Based on clinical experience from a CD33-targeting BiTE[®] for R/R AML, the day 1 dose is unlikely to have anti-leukemic effect and will be used

primarily to mitigate the risk of cytokine release syndrome following initiation of treatment

[figure not shown]
or exposure to higher concentrations of AMG 427 that are more likely to have anti-leukemic activity.

The proposed starting dose of AMG 427 in the FIH study is [REDACTED] μg . This was based on the predicted human dose necessary to provide a maximum serum concentration approximating 0.104 ng/mL, the mean in vitro EC_{50} of AMG 427-mediated CD69-upregulation, and is anticipated to have limited pharmacological activity. AMG 427 human PK profiles and exposures were predicted using a 2-compartment model with linear elimination from the central compartment. Human PK parameters were scaled using allometry from estimated PK parameters in cynomolgus monkey studies described in Section 2.2.2. Based on predicted AMG 427 PK, a starting dose of [REDACTED] μg following a short IV infusion (approximately 30 minutes to 1 hour) is predicted to achieve maximum serum concentrations approximating the mean EC_{50} of AMG 427 mediated CD69-upregulation in MOLM-13 cells (MABEL; 0.104 ng/mL). Of note, soluble FLT3 concentrations in the ranges observed in serum of AML patients (up to 140 ng/mL) did not have a significant effect on the predicted maximum serum concentrations of AMG 427 (within 2-fold) and were not used in the selection of the FIH starting dose. The use of the EC_{50} as the MABEL and basis for the FIH starting dose is supported by the previous and safe implementation of this strategy to identify the maximum recommended starting doses of previous bi-specific CD3-targeting molecules in clinical development (Saber et al, 2017).

Additionally, mean AUC from time zero to 72 hours ($\text{AUC}_{72\text{h}}$) and C_{max} exposures achieved at the HNSTD of the flat dose regimen of [REDACTED] $\mu\text{g}/\text{kg}$ in the 28-day toxicology study in cynomolgus monkeys were approximately 47-fold and 119-fold greater than human AUC from time 0 to 336 hours ($\text{AUC}_{336\text{h}}$) and C_{max} exposures predicted at the [REDACTED] μg starting dose, respectively, after correction for a 10-fold lower potency in cynomolgus monkey effector cells. Of note, relative to the step-dose regimen of [REDACTED] $\mu\text{g}/\text{kg}$ on day 1 followed by a step up to [REDACTED] $\mu\text{g}/\text{kg}$ on day 5, and another step up to [REDACTED] $\mu\text{g}/\text{kg}$ on day 8 and onwards ([REDACTED] $\mu\text{g}/\text{kg}$) also evaluated in the 28-day toxicology study, $\text{AUC}_{72\text{h}}$ and C_{max} exposures were approximately 6950-fold and 6180-fold greater than human exposure predictions, after a 10-fold potency correction (Table 3).

Subsequent planned escalations in AMG 427 dose up to [REDACTED] μg are shown in Table 3. At the highest planned clinical dose of [REDACTED] μg , the ratio of mean $\text{AUC}_{72\text{h}}$ and C_{max} exposures achieved at the [REDACTED] $\mu\text{g}/\text{kg}$ HNSTD in the 28-day toxicology study in cynomolgus

monkeys and predicted human AUC_{336h} and C_{max} exposures were approximately [REDACTED], respectively, after a 10-fold potency difference in human and cynomolgus monkey effector cells (ratio of mean AUC_{72h} and C_{max} exposures achieved at the [REDACTED] $\mu\text{g/kg}$ HNSTD in the 28-day toxicology study were approximately [REDACTED] and [REDACTED] respectively, after potency correction).

Minimally efficacious exposures of AMG 427 were estimated based on the in vitro assessments of AMG 427 activity. Based on the assessment of individual dose-response curves of AMG 427-mediated cell cytotoxicity in 7 different FLT3-expressing AML cell lines, a median EC_{90} of 12.1 pM (1.3 ng/mL) was calculated.

An AMG 427 dose of [REDACTED] μg is predicted to provide trough coverage of the EC_{90} following day 1 and day 5 administration and is expected to achieve anti-leukemic effect. As FLT3 expression is heterogeneous between different AML patients, AMG 427-mediated cytotoxicity in the least sensitive cell line (KG-1 cells) was also used to establish a conservative prediction of efficacy. Based on a mean EC_{90} of cell cytotoxicity in KG-1 cells (35.83 pM; 3.8 ng/mL), an AMG 427 dose of [REDACTED] μg is predicted to be efficacious. Collectively, minimally efficacious exposures of AMG 427 are predicted at doses of [REDACTED] μg , following once weekly administration.

As of **26 July 2021**, **53** subjects have been treated, **51** at **AMG 427** doses ranging from [REDACTED] μg in the ongoing FIH study, **and 2 subjects only receiving etanercept (Enbrel)**. Clinical data show an acceptable safety profile up to doses of [REDACTED] μg and preliminary PK analysis suggests dose-related increases in AMG 427 C_{max} and AUC across the dose range evaluated. The emerging clinical data from the ongoing FIH study support the exploration of additional dose levels **and regimens** to determine the MTD for AMG 427. Additional doses **and regimens** of [REDACTED] [REDACTED] μg will be explored in the dose escalation part of the study.

The eIV infusion group will enroll the first subjects, as eIV infusion is predicted to be the safest and most conservative dosing regimen (please see Section 3.1.1.2.1-Justification for eIV Investigational Product Dose). Two to 4 subjects will be initially enrolled for the [REDACTED] cohort. Overall, the dosing regimen will be as follows:

- **Day 1 and 2: eIV infusion of [REDACTED] μg (over approximately 48 hours)**
- **Day 3: eIV infusion of [REDACTED] μg (over approximately 24 hours)**
- **Day 5: short IV infusion of [REDACTED] μg (over approximately 90 minutes)**
- **Day 8: short IV infusion of [REDACTED] μg (over approximately 90 minutes)**

After Dose Level Review Team (DLRT) determines that the [REDACTED] μg target dose level and dosing route achieves an acceptable safety profile, then DLRT can recommend dose escalation and opening of additional experimental groups as described below.

2.5 Clinical Hypotheses

AMG 427 will demonstrate evidence of anti-leukemic activity at a safe and well-tolerated dose in subjects with MRD+ or R/R AML.

3. EXPERIMENTAL PLAN

3.1 Study Design

This is a FIH, open-label, phase 1 dose escalation study. AMG 427 will be evaluated as a short-term IV infusion (**eIV infusion may apply**) in adult subjects with MRD+ or R/R AML. The study will be conducted at approximately 15 sites in the US, Australia, Canada, Japan, South Korea, and Germany. Additional countries or sites may be added later.

The study will consist of up to a 14-day screening period, a treatment period, a safety follow-up period (SFU), and a long-term follow-up (LTFU) period (for subjects enrolled in the dose expansion phase only).

The dose-escalation cohorts will estimate the MTD, safety, tolerability, PK, and pharmacodynamics (PD) of AMG 427 in subjects with MRD+ or R/R AML using a Bayesian logistic regression model (BLRM: Neuenschwander et al, 2008). Planned dose levels (dose per infusion) for the dose-escalation cohorts are as follows: [REDACTED]

[REDACTED] µg (Table 4). Additionally, an option for cohort escalation will be available for confirming the safety in Japanese population, at sponsor discretion, for up to a maximum of 6 subjects. The sponsor will notify Japanese sites, if applicable, when the extended slots for a cohort are open for enrollment (after the Dose Level Review Team [DLRT] has confirmed the dose level is safe). The study will consist of 3 groups:

- **FIH Group**: AMG 427 administered as short term IV infusions in R/R AML subjects.
 - **(CLOSED)** Etanercept (Enbrel®) substudy: Etanercept will be administered for CRS prophylaxis 2 days prior to each cycle of AMG 427 short term IV infusions in R/R AML subjects in the US. (Etanercept may be implemented to FIH expansion groups based on emerging data).
- **eIV Infusion Group**: AMG 427 eIV infusions administered on days 1 and 2, and 3, with short term IV infusions on days 5 and 8 in R/R AML subjects. (eIV infusion may be implemented to FIH expansion groups based on emerging data).
- **MRD+ Group**: AMG 427 administered in short term IV infusions in MRD+ AML subjects.

At completion of the dose escalation cohorts, additional subjects (approximately 90 subjects, with approximately 40 subjects in the FIH cohorts and 50 subjects in the MRD+ groups) will be enrolled in a dose expansion cohort to gain further clinical experience, safety, and efficacy data in subjects with AMG 427.

3.1.1 Dose Escalation

The study will have 3 alternative dosing schedules:

- **(CLOSED)** Schedule A
 - D1/D5 or D1/D5/D12/D19 (dexamethasone prophylaxis)
- **(CLOSED)** Schedule B: Etanercept Substudy (R/R AML)
 - D1/D5 or D1/D5/D12/D19 (etanercept 2 days prior to each cycle).

The etanercept substudy used etanercept 2 days prior to infusion of each cycle D1, and if applicable, 2 days prior to infusion on D12. [REDACTED]

- **Schedule C** (Table 16 through Table 21): FIH, eIV (R/R AML); MRD+ Group (MRD+ AML)
 - D1/D3/D5/D8 or D1/D3/D5/D8/D12/D19 (dexamethasone prophylaxis)

Note:

- The MRD+ group will use Schedule C for all cycle collections and Table 22 for additional whole blood MRD collection, or Table 23, as applicable.

The initial cohort will begin with Schedule A and will receive 2 doses (1 each on D1 and D5). After reviewing the emerging PK, safety and efficacy data, the DLRT may recommend the administration of additional doses on D3 and D8, to comprise a 2-week cycle with doses on D1/D3/D5/D8 (Schedule C).

[figure not shown]
Additionally, if the following conditions are met, the DLRT may recommend the administration of 2 additional doses (D12 and D19):

- the 2-4 dose regimen (D1/D5 and/or D1/D3/D5/D8) is deemed safe and tolerable
- it is determined from the observed AMG 427 exposures that AMG 427 is rapidly cleared and/or distributed (ie, its observed half-life is much shorter than its predicted half-life)
- efficacy (based on clinical data and pharmacodynamic markers eg, clearance of FLT3⁺ blasts in the blood and/or bone marrow) is observed but is not sustained and addition of D12 and D19 doses may improve the duration or depth of response

Once the DLRT recommends additional doses, all subsequent cohorts will be treated with a 4 or 6 dose regimen in each cycle. The additional doses (if applicable), may be at

the same dose as the preceding dose or may be at higher doses (dose step). A dose step is any dose that is higher for a given subject than the subject has previously received. Dose steps may occur at D3, D5, D8, D12, or D19 infusions.

Starting with an initial lower dose may improve tolerability of subsequently administered higher doses due to initial reduction of the bulk of blast cells, thereby improving efficacy. The DLRT will recommend an initial lower dose, which will not be higher than dose which triggered a DLT. For a schematic overview of the different dose step options see [Figure 2](#) below.

Administration of a prophylactic steroid dose (8 mg IV dexamethasone) within 1 hour prior to start of AMG 427 dose on days 1, 3, 5, and 8 and prior to each dose step of AMG 427, to mitigate CRS, is mandatory. There is a \pm 1-3 day window for dosing visits.

[figure not shown]
Other dose level(s) of dexamethasone may be evaluated as necessary.

[figure not shown]
All other dosing rules, including dose limiting toxicities and treatment interruption, withholding, rechallenge, and permanent discontinuation apply as stated in Sections [6.2-6.6](#).

[figure not shown]
The estimate of the MTD(s), or the estimate of each MTD if step dosing is used, will use the BLRM design. Dose escalation will proceed using 2 parts: single subject cohorts and multiple subject cohorts.

[figure not shown]
3.1.1.1 FIH Group

The FIH group will evaluate AMG 427 administered as a short-term IV infusion in adult subjects with R/R AML. In escalation, approximately 90 subjects with R/R AML will be a part of FIH cohorts [REDACTED] (Table 4). Approximately 25 subjects with R/R AML will receive etanercept for CRS prophylaxis 2 days prior to their cycle and follow guidance below. **The option for group extension may be available, either at sponsor discretion or if recommended by the DLRT based on the review of the emerging safety data. The sponsor will notify sites, if applicable, when the extended slots for a group are open for enrollment after DLRT has confirmed the dose level is safe.**

3.1.1.2 eIV Infusion Group

The eIV group will evaluate AMG 427 administered as an eIV infusion in approximately 10 subjects with R/R AML. The study will be conducted in dose escalation, to explore and identify if alternative dosing of AMG 427 leads to an improved benefit/risk profile. The option for group extension may be available, either at sponsor discretion or if recommended by the DLRT based on the review of the emerging safety data. The sponsor will notify sites, if applicable, when the extended slots for a group are open for enrollment after DLRT has confirmed the dose level is safe. If improvement is seen in the benefit/risk profile for these subjects, eIV administration may be implemented in the ongoing FIH (short IV) dose escalation cohorts, as well as expansion cohorts.

Utilizing Schedule C, the eIV study design will consist of eIV and short IV infusions of AMG 427 administered on days 1 **and** 2, 3, 5, and 8.

- Days 1 and 2 will consist of the D1 dose administered as an eIV infusion over 48 hours (approximately 12-hour IV bag changes).
- Day 3 will consist of the D3 dose administered as an eIV infusion over 24 hours (approximately 12-hour IV bag changes).
- The remaining 2 doses (D5 and D8) will be regular short IV infusions (approximately 90 minutes) on day 5 and day 8.

The first eIV group will start at a DLRT-approved dose level from the FIH group as described in Section [6.2.1.1](#).

Subsequent eIV cohorts will use the same dose levels as the FIH (short IV) cohorts ([Table 4](#)). Dose escalation may occur if the DLRT deems that the eIV cohorts demonstrate a better benefit/risk profile than the equivalent FIH (short IV) cohorts. All other study processes remain unchanged. Data will be continuously evaluated, and DLRT may recommend dose schedule/level changes based on emerging PK data.

3.1.1.2.1 Justification for eIV Investigational Product Dose

Based on preliminary population pharmacokinetic analyses, AMG 427 C_{max} is predicted to be approximately 40% lower with a delayed T_{max} if infused over a 72 hour period, relative to the same total dose administered using a 1 hour infusion. It is hypothesized that the use of eIV infusions over a 72 hour period may reduce the intensity and/or frequency of the symptoms associated with CRS, relative to the same total dose of AMG 427 infused over a 1 hour duration. The DLRT may recommend modifying the dose or modifying the C1D1 eIV infusion time up to 7 days based on emerging safety and PK data.

3.1.1.3 MRD+ Group

The MRD+ group will evaluate AMG 427 administered as short IV infusions (90 minutes) in approximately 10 adult subjects with MRD+ AML. **The option for group extension may be available, either at sponsor discretion or if recommended by the DLRT based on the review of the emerging safety data. The sponsor will notify sites, if applicable, when the extended slots for a group are open for enrollment after DLRT has confirmed the dose level is safe.**

In escalation, subjects will be enrolled and start at a dose level from the FIH group that has been cleared by the DLRT as safe and tolerable. For example, if DLRT approves as safe and tolerable, the following dosing regimen **for FIH short term IV**: day 1: ■■■ μg, day 3: ■■■ μg, day 5: ■■■ μg, and day 8: ■■■ μg, the first MRD+ group 1 will be:

- Day 1: ■■■ μg
- Day 3: ■■■ μg
- Day 5: ■■■ μg
- Day 8: ■■■ μg

The escalation doses will follow [Table 4](#) and all escalation rules and study procedures remain unchanged. If an MTD/RP2D is not determined after approximately 10 subjects, DLRT may recommend additional subjects for dose escalation, which will follow the dose escalation in [Table 4](#).

3.1.2 Determination of Maximum Tolerated Dose

Dose escalation decisions will be made based on the recommendation of the BLRM model and the DLRT review after considering available safety, PK, PD, and efficacy data. The estimate of MTD will use the BLRM design. The model's estimated MTD dose is the dose with the highest probability of the target **toxicity probability interval (TPI)**, but with a less than 0.25 probability of an excessive or unacceptable TPI. The target TPI is (0.20, 0.33), and TPIs of (0.33, 0.60) and (0.60, 1.00) are defined as excessive and unacceptable, respectively. See [Section 3.4](#) for replacement of subjects.

Dose escalations will continue until either of the following occurs:

- No DLTs are observed on study and
- A minimum of 6 subjects are treated at the highest planned dose level.
- DLTs are observed on study and
- BLRM repeats the recommendation of a dose level (minimum of 6 treated subjects), or

- A maximum of 90 subjects are enrolled. If fewer than 6 subjects are treated at the MTD, additional subjects beyond 90 may be enrolled to confirm safety and tolerability.

The MTD is defined as the highest dose level whose DLT rate has the highest probability of the target TPI, an excessive/unacceptable TPI of < 0.25 , and a minimum of 6 subjects have been treated at the MTD.

Once the dose escalation phase has determined a final MTD or optimal RP2D, tocilizumab may be evaluated as an alternative prophylaxis to prevent/reduce the severity of CRS. A cohort of 3 subjects may be treated with AMG 427 at the final MTD dose level and a single dose of 8 mg/kg IV tocilizumab will be administered prior to the dose of AMG 427 replacing pretreatment with dexamethasone. If no DLTs are observed, 3 additional subjects will be included in this cohort. The use of tocilizumab may be further explored based on observed tolerability and other clinical and pharmacological data.

3.1.2.1 Maximum Tolerated Dose 1 (MTD1)

Dose escalation will proceed using 2 parts, single subject cohorts and multiple subject cohorts. In the single subject cohorts, single subjects will be enrolled at initial dose levels. When any pharmacologic activity (including, but not limited to, infusion reactions, cytokine release syndrome, decrease in peripheral blood blasts, or decrease in white blood cell count) is observed, the cohort size will be increased to multiple subject cohorts (N = 2 to 4 subjects). When the initial dose-limiting toxicity (DLT) is observed, the BLRM design will be used to guide dose level selection. After each cohort, the model's recommended MTD dose level for evaluation is the dose level with the highest probability of the target TPI, but with a less than 0.25 probability of an excessive or unacceptable TPI. The actual dose selected at each dose decision may be at or below the model's recommended dose as recommended by the DLRT after considering all information.

The dose escalation will be stopped when any of the following occurs:

- A minimum of 6 subjects have been treated at the MTD1 level
- When the sample size reaches 120 subjects
- Or as recommended by the DLRT after considering available safety, PK, PD, and efficacy data

[figure not shown]

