3.3 Number of Subjects

Participants in this clinical investigation shall be referred to as “subjects.”

It is anticipated that approximately 200 subjects will be enrolled in this study, with approximately 110 subjects enrolled in the dose escalation cohorts and 90 subjects in the dose expansion cohorts:

Dose escalation cohorts:

- FIH (R/R AML): approximately 90 subjects
 - **(CLOSED)** etanercept substudy (R/R AML): approximately 25 subjects
- eIV (R/R AML): approximately 10 subjects
- MRD Group (MRD+): approximately 10 subjects

Dose expansion cohorts:

- FIH (R/R AML): approximately 40 subjects
- MRD Group (MRD+): approximately 50 subjects

For ethical and operational reasons subjects who already are in the screening phase at the time of enrollment stop (end of expansion phase) will still be allowed to be treated. Therefore, an over running of subject recruitment might be possible.

Based on emerging data, additional subjects may be enrolled.

The rationale for the number of subjects is provided in Section [10.2](#).

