Appendix H. Two-Parameter BLRM Design

A 2-parameter Bayesian logistic regression model (BLRM, Neuenschwander et al, 2008) is used to guide dose escalation. The MTD target Toxicity Probability Interval (TPI) for DLT is (0.20, 0.33) and TPIs of (0.33, 0.60) and (0.60, 1.00) are defined as excessive and unacceptable, respectively. The design seeks to identify a dose most likely to have a DLT rate in the target TPI, but with overdose control that limits the possibility the dose has an excessive or unacceptable DLT rate (Babb et al, 1998). The probability of a DLT at dose level d_i is assumed to follow a Bernoulli distribution with probability p_i where the logit of p_i increases linearly with the log of the standardized dose in the following 2-parameter logistic model:

$$\log [p_i/(1-p_i)] = \text{logit}(p_i) = \log[a] + \exp(\log[b]) \log (d_i/d_{\text{ref}})$$

where a and b are random variables and d_{ref} is 1 of the planned dose selected as the reference dose.

A bi-variate normal prior distribution (Neuenschwander et al, 2008) was selected for $\theta = (\log a, \log b)$ where the probability that the true DLT rate is ≤ 0.40 at $\blacksquare \mu\text{g}$ is 0.90 and the probability the true DLT rate is ≤ 0.05 at the reference dose ($\blacksquare \mu\text{g}$) is 0.05. Additionally, the prior is such that p_i is approximately 0.05 for the $\blacksquare \mu\text{g}$ dose and 0.25 for the reference dose. Once the $\blacksquare \mu\text{g}$ is deemed safe by Dose Level Review Team (DLRT), the reference dose will be updated to the highest planned dose level.

The operating characteristics of the 2-parameter BLRM design were evaluated via simulation. The cohort size was fixed to 2 or 4 subjects. All simulated studies start with the multiple subject cohorts. The initial multiple subject dose level is $\blacksquare \mu\text{g}$ and subsequent doses were selected based on the following rules:

- After each cohort, the next dose is the one with the highest probability of the target TPI, but with a less than 0.25 probability of an excessive or unacceptable TPI.
- Skipping dose levels is not allowed.

Dose escalation was stopped given 1 or more of the following conditions:

- There have been at least 6 subjects treated at the dose recommended by the model.
- A maximum number of 36 subjects in the multiple subject cohorts is evaluated (note: this assumes that $n = 4$ subjects treated in single subject cohorts).

Operating characteristics are described below.

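### The cap that ends dose escalation is 90 subjects in Protocol Section 3.1.2 but 120 in Section 3.1.2.1, and neither section says whom it counts

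*Protocol*

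**What the plan says.** Protocol Section 3.1.2 sets out when escalation ends. In the branch that applies once DLTs have been observed there are two alternatives. Either the model repeats a dose recommendation with at least six treated, or "A maximum of 90 subjects are enrolled". An exception follows directly: "If fewer than 6 subjects are treated at the MTD, additional subjects beyond 90 may be enrolled to confirm safety and tolerability".

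Protocol Section 3.1.2.1, a subsection of the same rule headed MTD1, has its own list: "The dose escalation will be stopped when any of the following occurs". The three triggers are at least six subjects treated at MTD1, "When the sample size reaches 120 subjects", and a DLRT recommendation.

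Protocol Section 3.3 plans "approximately 110 subjects enrolled in the dose escalation cohorts and 90 subjects in the dose expansion cohorts". The first escalation line reads "FIH (R/R AML): approximately 90 subjects", with about 25 etanercept subjects as a sub-item. About 10 eIV and about 10 MRD+ subjects complete the list. The synopsis, Section 10.2 and SAP Section 3.2 give the same counts. The SAP states neither the 90 nor the 120.

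**The concern.** A maximum sample size in a first-in-human escalation is a pre-specified decision threshold. Sites, ethics committees and the DLRT rely on it as the limit on exposure before expansion begins. Here a general rule and its own subsection give different limits, 30 subjects apart.

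The scope of each figure is also open. Section 3.1.2 does not say whether 90 means FIH subjects or everyone in escalation. Section 3.1.2.1 speaks only of the sample size, and the restriction to MTD1 comes from its heading. The protocol expects two to three MTDs, and MTD2 escalation begins only after MTD1 is determined. It therefore matters whether a cap covers MTD1 alone or all stages together. Section 3.1.1.3 applies the same escalation rules to the MRD+ group, so it is unclear whether those subjects count towards 90, towards 120 or towards neither.

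The branch of Section 3.1.2 that contains the 90 is in force: the Amendment 5 rationale in the protocol already reports one DLT.

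**Working it through.** **Inputs**

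- General cap: 90 (Protocol 3.1.2, DLT branch)
- MTD1 cap: 120 (Protocol 3.1.2.1)
- Planned escalation: FIH 90, including etanercept 25; eIV 10; MRD+ 10 (Protocol 3.3)
- Planned expansion: 40 + 50 = 90 (Protocol 3.3)

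**Step 1. Reproduce the planned sizes.**

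- Escalation with etanercept nested in FIH: 90 + 10 + 10 = 110, which matches the stated 110.
- Study total: 110 + 90 = 200, which matches the stated 200.
- Counting etanercept separately gives 90 + 25 + 10 + 10 = 135, which does not match. Section 10.2 lists the four groups on one line, but the stated 110 and the sub-item layout in Section 3.3 show that etanercept is part of FIH.

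**Step 2. Compare the caps with each other.**

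120 − 90 = 30 subjects, and 30/90 = 33% above the Section 3.1.2 figure.

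**Step 3. Compare each cap with the plan under both readings of scope.**

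| Cap | If it counts FIH only (plan 90) | If it counts all escalation groups (plan 110) |
|---|---|---|
| 90 | equal to plan | 110 − 90 = 20 below plan |
| 120 | 120 − 90 = 30 above plan | 120 − 110 = 10 above plan (10/110 = 9%) |

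The 90 fits the plan if it means FIH. The 120 exceeds the plan on either reading. Since it sits under MTD1, a limit for one stage is larger than the plan for the whole escalation phase, and it cannot bind within planned enrolment.

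**Step 4. Study total if 120 were reached.**

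- 120 covers all escalation groups: 120 + 90 = 210
- 120 covers FIH only: 120 + 10 + 10 + 90 = 230

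The range is 210 to 230 against about 200.

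**Step 5. Read the two rules side by side between 90 and 120.**

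Take the same count under both sections, with DLTs observed and at least six subjects treated at the MTD, so that the Section 3.1.2 exception does not apply. At 91 subjects Section 3.1.2 has already ended escalation, while the numerical trigger in Section 3.1.2.1 has not been met.

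**The case against.** Much of the case for leniency stands, and it limits what can be concluded.

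A reader might infer that the protocol orders escalation both to stop at 90 and to carry on to 120. It does not. Section 3.1.2.1 lists alternative stop triggers and never requires enrolment to continue. A trial that stops at 90 breaches neither section. The fault is an inconsistent ceiling, not an impossible instruction.

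Nor is 90 absolute. It sits in the DLT branch and may be exceeded when fewer than six have been treated at the MTD. One could suppose that 120 is an outer limit for that case. The documents do not say so: the exception names no figure, and the 120 carries no such condition.

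A reader might also infer that 120 makes the planned total of 200 impossible. That goes too far. The 200 is approximate, and Section 3.3 allows over-running and further enrolment on emerging data. Sections 3.1.1.1 to 3.1.1.3 allow group extensions without a number. A ceiling of 120, if reached, would exceed the target; it does not falsify it. Equally, this flexibility in planned enrolment does not reconcile two different stopping thresholds.

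Finally, Appendix H has the words "A maximum number of 36 subjects in the multiple subject cohorts is evaluated", with four more assumed in single-subject cohorts (36 + 4 = 40). It is tempting to read 40 as a third cap. It is a setting of the simulations, not a rule for running the trial.

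The practical effect may also be small: the six-subject trigger or the DLRT may end escalation first, and no analysis in the SAP depends on either cap.

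**Conclusion.** The inconsistency is real. Two sections in current text give caps of 90 and 120, a gap of 30 subjects (33%), and no text explains the larger one. The 120 is above planned enrolment whichever groups it counts, by 30 for FIH or by 10 for all escalation. It therefore does no work as a limit within the plan. If reached, it would take the study to between 210 and 230 subjects; the spread reflects only the unstated scope.

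This rests on three readings: that etanercept is nested within FIH, which reproduces the stated 110; that DLTs have been observed, so the 90 branch applies; and that the exception for fewer than six at the MTD is not in play. The planned sizes are approximate, so the comparisons with 90, 110 and 200 are with targets, not fixed limits. The direct conflict between the two caps does not depend on those targets, although the undefined scope leaves open whether both count the same subjects.

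**What to change.** Reconcile Protocol Sections 3.1.2 and 3.1.2.1 to one cap that agrees with Sections 3.3 and 10.2. The figure 90 matches the stated FIH size. If 120 is intended, the planned escalation and total numbers should be restated to fit it in the synopsis, Protocol Sections 3.3 and 10.2, and SAP Section 3.2.

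In the same edit:

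- Keep or restate the exception for fewer than six subjects at the MTD, so that it is clear whether it applies to the reconciled cap.
- Say which groups the cap counts: FIH only, or FIH with eIV and MRD+.
- Say which stages it counts: MTD1 alone, or MTD1 to MTD3 together.

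If the planned numbers stay as they are, the cost is protocol wording only, and the SAP needs no change because it states neither cap. Choosing 120 also means revising the sample-size text in both documents.
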